## 5 Treatment

### 5.1 Study treatment

#### 5.1.1 Investigational and control drugs

All eligible subjects will be randomized to receive either sacubitril/valsartan or enalapril. The following study treatment will be provided:

**Table 5-1 Investigational and comparator treatment during the double-blind epoch**

Treatment Arm	Number of Subjects	Minimum dose	Maximum dose	Frequency	Formulation	Administration Route
sacubitril/valsartan*	68	24/26 mg	97/103 mg	BID	Tablet	Oral
sacubitril/valsartan matching placebo						Oral
enalapril	68	2.5 mg	10 mg	BID	Tablet	Oral
enalapril matching placebo						Oral

\*Investigational product labeling for sacubitril/valsartan dose levels is based on the total contribution of both components of sacubitril/valsartan and reads, 50 mg, 100 mg and 200 mg. This is equivalent to the sacubitril/valsartan dose levels 24/26 mg, 49/51 mg and 97/103 mg, respectively.

**Table 5-2 Treatment dose levels during the double-blind epoch**

Dose Level	Sacubitril/valsartan*	Enalapril
1	24/26 mg or matching placebo BID	2.5 mg or matching placebo BID
2	49/51 mg or matching placebo BID	5 mg or matching placebo BID
3	97/103 mg or matching placebo BID	10 mg or matching placebo BID

Dose Level	Sacubitril/valsartan*	Enalapril
*Investigational product labeling for sacubitril/valsartan dose levels is based on the total contribution of both components of sacubitril/valsartan and reads, 50 mg, 100 mg and 200 mg. This is equivalent to the sacubitril/valsartan dose levels 24/26 mg, 49/51 mg and 97/103 mg, respectively.		

Both sacubitril/valsartan and enalapril and their matching placebos will be packaged and labeled by the sponsor in accordance with the US Code of Federal Regulations governing handling of investigational treatments, and will be dispensed by the study physician.

Sacubitril/valsartan and enalapril will be packaged separately to limit the number of pack types which will allow more flexibility in the drug supply process to cover all the different treatment possibilities (treatment arm and medication dose level), see [Table 5-2](#) and [Table 5-4](#).

Packaging type is described below:

- sacubitril/valsartan and its matching placebo will be provided in high-density polyethylene (HDPE) bottles.
- enalapril 2.5 mg and its matching placebo will be provided in HDPE bottles.
- enalapril 5 mg and 10 mg and its matching placebos will be provided in blister packs.

Each participating site will be provided with an investigational drug supply containing Dose Levels 1, 2, 3 and their matching placebos. Bottles and blister packs will be numbered and assigned via an interactive response technology (IRT). Treatment for the day of randomization and all visits forward will be assigned via IRT.

All subjects will begin the study on Dose Level 1. At each subsequent study visit during the double-blind epoch, the study physician will sequentially up-titrate the study drug dose (based on clinical tolerance and the USPI) to achieve the desired dose of Dose Level 3 (97/103 mg sacubitril/valsartan BID or 10 mg enalapril BID).

Subjects not tolerating escalation from Dose Level 1 to Dose Level 2 (or Dose Level 2 to Dose Level 3) can be titrated down to the next lower Dose Level (including active medication and matching placebos), if, in the investigator's judgement, the adjustment/elimination of concomitant medications is not possible or does not alleviate the side effects of concern. See [Section 5.5.5](#).

This study is designed as a double-blind, double-dummy trial to ensure blinding during the entire course of the study. To maintain the blinding, subjects will be required to take their assigned active treatment tablet along with placebo matching the opposite treatment twice daily.

**Table 5-3** **Investigational treatment during the open label epoch**

Treatment	Number of subjects	Minimum dose*	Maximum dose	Frequency	Formulation	Route
Open-label (sacubitril/valsartan)	136	24/26 mg	97/103 mg	BID	Tablet	Oral

\*sacubitril/valsartan 24/26 mg BID (Dose Level 1) will be given to subjects who completed the double-blind treatment epoch on Dose Level 1 and is also available if down-titration is required.

**Table 5-4 Treatment Dose Levels during the open-label epoch**

Dose Level*	Sacubitril/valsartan
1	24/26 mg BID
2	49/51 mg BID
3	97/103 mg BID

\*sacubitril/valsartan 24/26 mg BID (Dose Level 1) will be given to subjects who completed the double-blind treatment epoch on Dose Level 1 and is also available if down-titration is required.

Open-label sacubitril/valsartan will be packaged and labeled by the sponsor in accordance with the US Code of Federal Regulation governing handling of investigational treatments, and will be dispensed by the study physician. Open-label treatment will be provided for 8 weeks.

All subjects entering the open label-treatment epoch will be given sacubitril/valsartan 49/51 mg BID (Dose Level 2) unless they completed the double-blind treatment epoch on Dose Level 1. Instead, these subjects will enter the open-label epoch on sacubitril/valsartan 24/26 mg BID dose (Dose Level 1). At each subsequent study visit during the open-label epoch, the study physician will sequentially up-titrate the study drug dose (based on clinical tolerance and the USPI) to achieve the targeted desired dose of 97/103 mg sacubitril/valsartan BID (Dose Level 3).

During the open label phase, patients not tolerating the escalation from Dose Level 1 to Dose Level 2 (or Dose Level 2 to Dose Level 3) can be titrated down to the next lower Dose Level, if, in the investigator's judgement, the adjustment/elimination of concomitant medications is not possible or does not alleviate the side effects of concern. See [Section 5.5.5](#).

### **5.1.2 Additional treatment**

The protocol requires subjects to continue their current heart failure drug therapy, during the 2-week baseline phase.

## **5.2 Treatment arms**

Subjects will be assigned at Day 1 to one of the following two treatment arms in a 1:1 ratio:

- sacubitril/valsartan; or,
- enalapril

Subjects will be assigned at Week 8 to open label extension phase during which all subjects will receive:

- sacubitril/valsartan

### **5.3 Treatment assignment and randomization**

At visit 3 all eligible subjects/subjects will be randomized via Interactive Response Technology (IRT) to one of the treatment arms. The investigator or his/her delegate will contact the IRT after confirming that the subject fulfills all the inclusion/exclusion criteria. The IRT will assign a randomization number to the subject, which will be used to link the subject to a treatment arm and will specify a unique medication number for the first package of study drug to be dispensed to the subject.

The randomization numbers will be generated using the following procedure to ensure that treatment assignment is unbiased and concealed from subject and investigator staff. A subject randomization list will be produced by the IRT provider using a validated system that automates the random assignment of subject numbers to randomization numbers. These randomization numbers are linked to the different treatment arms, which in turn are linked to medication numbers. A separate medication list will be produced by or under the responsibility of Novartis Drug Supply Management using a validated system that automates the random assignment of medication numbers to packs containing the investigational drug(s).

The randomization scheme for subjects will be reviewed and approved by a member of Biometrics USCDMA.

### **5.4 Treatment blinding**

Subjects, investigator staff, persons performing the assessments, data analysts and the Clinical Trial Team (CTT) will remain blind to the identity of the treatment from the time of randomization until database lock, using the following methods: (1) Randomization data are kept strictly confidential until the time of unblinding, and will not be accessible by anyone else involved in the study with the exception of the IRT provider generating the randomization code. (2) The identity of the treatments will be concealed by the use of investigational treatments that are identical in packaging, labeling, and schedule of administration, appearance, taste and odor.

A double-dummy design is used because the identity of the study drug cannot be disguised, as the drug products are visibly different. To maintain the blinding, subjects will be required to take their assigned active treatment tablet along with placebo matching the opposite treatment twice daily.

Unblinding will only occur in the case of subject emergencies (see [Section 5.6](#)) and at the conclusion of the study.

### **5.5 Treating the patient**

Sponsor qualified medical personnel will be readily available to advise on trial related medical questions or problems.

#### **5.5.1 Subject Numbering**

Each subject is uniquely identified in the study by a combination of his/her center number and subject number. The center number is assigned by Novartis to the investigative site. Upon signing the informed consent form, the subject is assigned a subject number by the investigator. At each site, the first subject is assigned subject number 1, and subsequent subjects are assigned

consecutive numbers (e.g. the second subject is assigned subject number 2, the third subject is assigned subject number 3). The investigator or his/her staff will contact the IRT and provide the requested identifying information for the subject to register them into the IRT. Only the assigned subject number must be entered in the field labeled “Subject ID” on the EDC data entry screen (e.g. enter ‘1’, ‘2’, etc.). Once assigned to a subject, the subject number will not be reused. If the subject fails to be randomized for any reason, the IRT must be notified within 2 days that the subject was not randomized.

### **5.5.2 Dispensing the study drug**

Each study site will be supplied with study drug in packaging of identical appearance.

Novartis will supply each study site with the randomized and open-label treatment in clinical trial packaging. The study drug packaging has a 2-part label. A unique randomization number is printed on each part of this label which corresponds to one of the “n” treatment arms and a [specific visit or dose/dose level]. Investigator staff will identify the study drug package(s) to dispense to the subject by contacting the IRT and obtaining the medication number(s). Immediately before dispensing the package to the patient, investigator staff will detach the outer part of the label from the packaging and affix it to the source document (Drug Label Form) for that subject’s unique subject number.

### **5.5.3 Handling of study and additional treatment**

No additional treatment is provided as part of the study

#### **5.5.3.1 Handling of study treatment**

Study treatment must be received by a designated person at the study site, handled and stored safely and properly, and kept in a secured location to which only the investigator and designees have access. Upon receipt, all study treatment must be stored according to the instructions specified on the labels. Clinical supplies are to be dispensed only in accordance with the protocol. Technical complaints are to be reported to the respective Novartis CPO Quality Assurance. Medication labels will include storage conditions but no information about the subject except for the medication number.

The investigator must maintain an accurate record of the shipment and dispensing of study treatment in a drug accountability log. Monitoring of drug accountability will be performed by monitors during site visits or remotely and at the completion of the trial. Subjects will be asked to return all unused study treatment and packaging at the end of the study or at the time of discontinuation of study treatment.

At the conclusion of the study, and as appropriate during the course of the study, the investigator will return all unused study treatment, packaging, drug labels, and a copy of the completed drug accountability log to the Novartis monitor or to the Novartis address provided in the investigator folder at each site.

#### **5.5.3.2 Handling of additional treatment**

Not applicable.

#### **5.5.4 Instructions for prescribing and taking study treatment**

Novartis will supply the investigators with all medications sufficient for the course of the study. Subjects will be provided with medication packs containing study drug corresponding to their assigned treatment arm and dose level, sufficient to last until the next scheduled visit. Study medication should be taken with a glass of water with or without food. If the patient misses taking any study drug dose, he/she should take it as soon as possible, unless it is within 4 hours for the following scheduled dose. In this case, the patient should skip the missed dose and return back to his/her regular study drug administration schedule.

In order to adequately blind the study, patients will be required to take their assigned active treatment tablet along with placebo matching the opposite treatment twice daily. Subjects will be instructed to take a total of two tablets by mouth twice a day for the duration of the double-blind treatment epoch, as follows:

- One tablet from the sacubitril/valsartan – sacubitril/valsartan matching placebo pack, and;
- One tablet from the enalapril - enalapril matching placebo pack

[Table 5-5](#) summarizes the study drug that will be taken during the double-blind treatment epoch by visit and [Table 5-6](#) summarizes the study drug that will be taken during the open-label treatment epoch.

Forced-titration will proceed according to the following table:

**Table 5-5 Study drug dispensed during double-blind treatment epoch**

Visit	Dose Level	SacubitriI/valsartan**	Enalapril	Route	Timing
Rando/Visit 3	1 a,b	24/26 mg or matching placebo BID	2.5 mg or matching placebo BID	Oral	AM & PM
Week 2/Visit 5	2 c/d	49/51 mg / 97/103 mg or matching placebo BID	5 mg or matching placebo BID	Oral	AM & PM
Week 4/Visit 6	2 c/d	49/51 mg / 97/103 mg or matching placebo BID	10 mg or matching placebo BID	Oral	AM & PM

\*\*Investigational product labeling for sacubitriI/valsartan dose levels is based on the total contribution of both components of sacubitriI/valsartan and reads, 50 mg, 100 mg and 200 mg. This is equivalent to the sacubitriI/valsartan dose levels 24/26 mg, 49/51 mg and 97/103 mg, respectively.

a. Initial starting dose (Level 1) Eligible patients will be randomized via IRT to either sacubitriI/valsartan or enalapril, Dose Level 1.

b. Available after Rando/Visit 3 to end of double-blind treatment epoch only if Dose Levels 2 and 3 are not tolerated despite modification of other non-disease-modifying HF medications and re-challenge.

c. Only if Dose Level 3 is not tolerated despite modification of other non-disease-modifying HF medications and re-challenge.

d. This target Dose Level must be maintained for as long a duration as possible. If down-titration is necessary due to side effects, the patient should be re-challenged as soon as medically possible per the investigator's judgment.

- At Randomization on Day 1 (Visit 3, enrolled subjects will be randomized via IRT to either sacubitriI/valsartan or enalapril. All subjects will start at Dose Level 1 (2.5 mg enalapril or 24/26 mg sacubitriI/valsartan, BID).
- At Week 1 (Visit 4), subjects will have a telephone visit.
- At Week 2 (Visit 5), subjects will be force-titrated to the next dose, Dose Level 2 (5 mg enalapril or 49/51 mg sacubitriI/valsartan, BID) or Dose Level 3 (10 mg enalapril or 97/103 mg sacubitriI/valsartan, BID) and remain on this dose through the evening dose prior to Week 4 (Visit 6).
- At Week 4 (Visit 6), subjects will be force-titrated to the next dose, Dose Level 2 (5 mg enalapril or 49/51 mg sacubitriI/valsartan, BID) or Dose Level 3 (10 mg enalapril or 97/103 mg sacubitriI/valsartan, BID) and remain on this dose through the evening dose prior to Week 8 (Visit 8).
- At Week 6 (Visit 7), subjects will have a telephone visit.
- All subjects that complete the 8 week double-blind treatment epoch will proceed into the 8-week open-label epoch on sacubitriI/valsartan.
- At Week 8 (Visit 8), Drug accountability will be performed and all double-blind treatment medication will be returned to the site.

- Open-label sacubitril/valsartan will be dispensed at Week 8 (Visit 8) with subject's instructions **NOT** to start their open label-treatment until after completing a 36-hour wash out. All patients will have the wash out in order to maintain the blinding of the core study.

All dose levels will be available throughout the study. Dose adjustments to lower dose levels may be made at any time at both scheduled and unscheduled visits only if indicated for blood pressure control/tolerability reasons.

All study treatment assigned by the IRT will be recorded/databased in the IRT.

All dosages prescribed and dispensed to the subject and all dose changes during the study must be recorded in the IRT and on the Dosage Administration Record eCRF.

Study medication should be taken twice daily with a glass of water with or without food.

If the subject misses taking any study drug dose, he/she should take it as soon as possible and within 4 hours of the scheduled dose time. If the patient is unable to take the missed dose within 4 hours of the scheduled dose time, he/she should skip the missed dose and return back to his/her regular study drug administration schedule.

The investigator must promote compliance by instructing the subject to take the study treatment exactly as prescribed and by stating that compliance is necessary for the subject's safety and the validity of the study. The subject must also be instructed to contact the investigator if he/she is unable for any reason to take the study treatment as prescribed.

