**3. Further Adjust Study Treatment Dose Level**

- If tolerability issues are not alleviated despite down-titration by one dose level, the investigator may down-titrate further to the next lower study treatment dose level. The subject may continue receiving the lower dose level for a recommended period of 1 to a maximum of 4 weeks. See Step 5.
- Again, once stable, the subject should be re-challenged with up-titration to the next higher dose level in an attempt to gradually bring the subject back to the target study treatment dose level (Dose Level 3).
- The investigator may choose the next dose level for down- or up-titration according to his or her clinical judgment.

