1.1 Study design

This study is a multicenter, randomized, double-blind, double dummy, parallel group, active-controlled 8-week study with open-label extension using medical device-grade patient worn sensors to measure waking and sleeping physical activity in the ambulatory outpatient setting. The 18-week study duration will consist of a 2-week baseline observation phase (with patients continuing their current heart failure [HF] drug therapy), followed by an 8-week blinded treatment phase during which approximately 136 patients will be randomized to either initiation of sacubitril/valsartan treatment or enalapril comparator in a 1:1 ratio with no stratification at approximately 25-30 centers in the United States, and finally an 8-week open-label extension phase during which all patients will be treated with sacubitril/valsartan.

Each patient will undergo a 36-hour washout period (during which angiotensin converting enzyme inhibitor [ACEi], or study drug will be withheld) before the start of the randomized, blinded treatment phase, and again before beginning the open-label extension phase to ensure that the blinding of the core study is maintained and to reduce the risk of angioedema.

Patients will be randomized to either sacubitril/valsartan 24/26 mg bis in diem/twice a day (BID) or enalapril 2.5 mg BID (Dose Level 1). At each subsequent study visit during the double-blind epoch, the study physician will sequentially up-titrate the study drug dose (based on clinical tolerance and the United States Package Insert [USPI]) to achieve the desired dose of sacubitril/valsartan 97/103 mg BID or enalapril 10 mg BID (Dose Level 3). Dose level 2 is defined as sacubitril/valsartan 49/51 mg BID or enalapril 5 mg BID. Patients not tolerating escalation from Dose Level 1 to Dose Level 2 (or Dose Level 2 to Dose Level 3) can be titrated down to the next lower Dose Level (including active medication and matching placebos), if, in the investigator's judgement, the adjustment/elimination of concomitant medications is not possible or does not alleviate the side effects of concern.

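### The Week 2 dosing instruction lets subjects go from Dose Level 1 straight to Dose Level 3, although the protocol and SAP both require stepwise up-titration

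*Protocol*

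**What the plan says.** The general rule is in Protocol 5.1.1, in the text after Table 5-2. It sets the starting dose, "All subjects will begin the study on Dose Level 1", and then provides that at each later double-blind visit "the study physician will sequentially up-titrate the study drug dose" toward Level 3. The accompanying tolerance rule recognises only single steps: "Subjects not tolerating escalation from Dose Level 1 to Dose Level 2 (or Dose Level 2 to Dose Level 3) can be titrated down". SAP 1.1 carries the same stepwise rule.

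The visit-by-visit instruction is in Protocol 5.5.4, below Table 5-5. For Week 2 it reads "At Week 2 (Visit 5), subjects will be force-titrated to the next dose, Dose Level 2". After giving the Level 2 doses, the sentence adds Level 3 (enalapril 10 mg or sacubitril/valsartan 97/103 mg BID) as an alternative, and the subject stays on the chosen dose until Week 4. The Week 4 bullet gives the same two options.

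Footnote c to Table 5-5, attached to Level 2, reads "Only if Dose Level 3 is not tolerated despite modification of other non-disease-modifying HF medications and re-challenge".

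**The concern.** The Week 2 bullet is the line a site follows on the day. It conflicts with the stepwise rule in Section 5.1.1 and SAP 1.1. It also conflicts with itself, since the next dose after Level 1 can only be Level 2. It gives no criterion for choosing between the two levels, so two sites could dose similar subjects differently and both claim adherence.

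The stakes are tolerability and consistent exposure. Section 3.6 names renal dysfunction, hyperkalemia and hypotension as the main risks of sacubitril/valsartan. It cites up-titration at set weeks as a mitigation and says ACEi- or ARB-naive subjects are at greater risk. No inclusion criterion in Section 4.1 requires earlier ACEi or ARB use, and SAP 2.4.2 has a never-exposed category. Such subjects can therefore be enrolled, and the bullet does not exempt them from a direct move to Level 3.

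**Working it through.** The plan states no figure to reproduce. The check follows the dose level through the visits and then compares step sizes.

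**Visit trace** (Table 6-1 and Section 5.5.4)

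| Visit | Day | Titration marked? | Stepwise rule (5.1.1, SAP 1.1) | 5.5.4 bullets |
|---|---|---|---|---|
| 3 | 1 | No (start) | Level 1 | Level 1 |
| 4 | 7 | No (telephone) | Level 1 | no dose change |
| 5 | 14 | Yes | Level 2 | Level 2 **or Level 3** |
| 6 | 28 | Yes | Level 3 if Level 2 is tolerated | Level 2 or Level 3 |

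The titration row of Table 6-1 marks Visits 5, 6, 8, 10 and 11, which match weeks 2, 4, 8, 10 and 12 in Section 3.6. Nothing scheduled before Visit 5 raises the dose, so at Week 2 the Level 3 option skips a level. At Week 4 the two options fit stepwise titration: Level 3 for a subject on Level 2, and Level 2 for a subject still on Level 1. That bullet is not in dispute.

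**Step size** (doses from Table 5-2; sacubitril/valsartan by labelled total of 50, 100 and 200 mg)

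- Sacubitril/valsartan: 100/50 = 2; 200/100 = 2; skipping, 200/50 = 4.
- Enalapril: 5/2.5 = 2; 10/5 = 2; skipping, 10/2.5 = 4.

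**Time on Level 2 before Level 3**

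- Stepwise: 28 − 14 = 14 days. With the ±3-day visit window in Section 6, this runs from 25 − 17 = 8 to 31 − 11 = 20 days.
- Skipping: 0 days.

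**Is the skip needed to reach target?** Level 1 to Level 3 takes 2 steps, and there are 2 double-blind titration visits before Week 8 (Visits 5 and 6). Stepwise titration reaches Level 3 at Day 28 and leaves 56 − 28 = 28 days on it. So the skip is not needed.

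**Subjects exposed to the ambiguity.** Minimum 0, maximum 68 + 68 = 136. The documents give nothing to narrow this range.

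**Does other text authorise the skip?** Section 5.5.5, step 3 says "The investigator may choose the next dose level for down- or up-titration according to his or her clinical judgment", but it belongs to the sequence for tolerability problems, after a down-titration, and does not govern the routine first step. Section 5.5.4 allows dose changes at any visit, but only downward. Section 5.5.5, step 5 allows titration every 1 to 4 weeks after an interruption, so a subject who interrupted early might be on Level 2 by Week 2; the bullet is not limited to such subjects.

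**Two points not relied on.** Footnote c could be read as barring Level 2 until Level 3 has been tried, but it can also be read, like footnote b, as a rule for staying on or returning to a lower level. Table 5-5, as extracted, shows enalapril 5 mg only at Week 2 and 10 mg only at Week 4, beside both sacubitril/valsartan strengths. This may be an extraction fault.

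**The case against.** The best case on the other side is that this is loose drafting and not an instruction to skip. The phrase about the next dose governs the sentence, the same two-level list recurs at Week 4, and Section 5.1.1 makes titration depend on clinical tolerance and the USPI. A sensible investigator would go to Level 2. Safeguards also exist: the potassium, renal and blood pressure criteria in Table 5-7, laboratory tests at Visit 5 itself, and freedom to reduce the dose at any visit. Section 3.6 speaks of appropriate up-titration without specifying one level per visit. The USPI is not available here, so whether it would bar the skip is unknown. No harm or effect on the trial's inference has been shown.

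Much of this stands as a limit on the consequence. The safeguards reduce the risk, the number affected is unknown, and the 14 days is nominal. It does not remove the conflict. The bullet names Level 3 and its doses explicitly at a visit that subjects on the planned course reach on Level 1. The tolerance clause qualifies stepwise titration, so it cannot be the authority for abandoning it.

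**Conclusion.** The concern holds. As written, the Week 2 bullet permits a one-step move from Level 1 to Level 3 that Protocol 5.1.1 and SAP 1.1 do not allow. The step is 4-fold instead of 2-fold in either arm and removes the nominal 14 days on Level 2. The conclusion rests on the prose of the bullet and on the visit schedule, and it assumes a subject on the planned course with no earlier interruption. It should be fixed because it is an operative dosing rule in a population that may include ACEi/ARB-naive subjects. No effect on the primary estimate, blinding, power or error rate is claimed.

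**What to change.** 1. In the Week 2 bullet and the Week 2 row of Table 5-5, give Level 2 only (49/51 mg or 5 mg) for both arms.
2. At Week 4, give the next level up: Level 3 (97/103 mg or 10 mg) for subjects tolerating Level 2, and Level 2 for subjects still on Level 1.
3. Limit footnote c to continuing on, or returning to, Level 2 after Level 3 has been tried.
4. Check the enalapril cells of Table 5-5 against the original page, and confirm that the IRT assigns doses accordingly.
5. If Level 3 at Week 2 is intended for some subjects, say so in Section 5.1.1 and SAP 1.1.

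The cost is a short text correction, an IRT configuration check and a letter to sites. Under Section 11.1 the correction must go through a written amendment approved by the sponsor, the IRB/IEC and, where required, health authorities. Sample size, visit schedule and analysis do not change.
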